5.6 Duration of follow-up

Patients will be followed for approximately 6 months at The Ohio State University Wexner Medical Center.

5.7 Criteria for removal from study

Patients will be removed from the study by patient preference or MD request otherwise will remain on study for 6 months.

5.8 Travel Re-imbursement

Patients who elect to become vendors [**APPENDIX O**] of The Ohio State University will be paid \$25 (a maximum of twice monthly) for each physical therapy visit at a total of \$200, if they complete all 8 visits. Payment will be given in cash at the time of the physical therapy visit. If patients are scheduled for additional physical therapy sessions, as prescribed by their physical therapist in accordance with routine care, patients will be reimbursed at only one physical therapy appointment, per week, every other week of the month.

6.0 STATISTICAL CONSIDERATIONS

6.1 Primary Endpoint

The primary endpoint is feasibility, defined by 80% of eligible participants completing the Otago Exercise Programme (OEP). Program completion is the primary indicator of this feasibility pilot project. 80% completion was chosen based upon the Otago Exercise Programme controlled trials, where the effectiveness of home based exercise to reduce falls in injuries in elderly adults in the community had a 90% completion rate of the trial.⁵³ When the Otago Exercise Programme was delivered in different centers 87% of participants

completed the trial⁵⁴. When the Otago Exercise Programme was introduced into the primary care practice, older adults (>80) approximately 47% participation occurred and 79% completed one year assessments 55. Therefore, 80% completion was chosen as the feasibility endpoint to achieve the desired effects of improving strength and balance via OEP.

We will describe the proportion of screened patients who agree to participate, the proportion of patients who attend certain percentage of assigned PT sessions and the proportion of patients who complete the whole study along with respective 95% confidence intervals. Study implementation and challenges will be evaluated by patient exercise logs. Exercise levels at home will also be assessed by exercise diary log. Adverse events (AE) and their severity will be captured according to the CTCAE v4.0, and whether any AEs can be attributed to exercise.

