1.2 Primary Objective

To assess the feasibility of implementing a structured exercise program by evaluating recruitment and retention, exercise program adherence, sustainability, adverse events, and implementation challenges.

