3.0 METHODS

3.1 Patient Selection

Patients will be recruited from the hematology clinics at The Ohio State University. Patients who are undergoing an evaluation for treatment and, or are being treated for a hematologic malignancy are referred by their treating care team for participation in the study. These patients will receive information regarding the proposed study, and will be asked if they would like to undergo screening for their current level of fitness to determine eligibility for study participation. Those agreeing to be screened will sign the study consent and HIPAA forms. They will then undergo the SPPB evaluation. Patients whose total score on the SPPB is ≤ 9 , and who meet all other inclusion criteria, will be deemed eligible to continue in the study. Eligible patients who have consented to participate in this study will be assigned a study ID. A peripheral blood sample will also be collected from them for research purposes (See Section 6.0).

Failed screening (i.e. >9 on SPPB) will be captured as part of feasibility. In addition, reasons why patients decline participation will be tracked without documenting patient identifiers [**APPENDIX A**]. For example, patient declined enrollment due to physical activity being judged as too difficult.

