3.4 Informed Consent

Discussions between the study coordinators and/or medical oncologists and study participants will occur in clinic. The study coordinators will address all questions regarding the study and consent form and emphasize that the participant can withdraw from the study at any point in time. If patients are interested in participating in the study and meet all eligibility criteria, they will sign the consent form and then be assessed for eligibility and, when applicable, register as detailed below.

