4.4 Information-Motivation-Behavioral Model and Self Efficacy Schema

4.5 Study Measures

4.5.1 Short Physical Performance Battery (SPPB)

At the time of screening patients will undergo a SPPB [APPENDIX F]; patients with a SPPB score of <9 will be allowed to enroll in the study. Patients will complete an SPPB at the completion of the OEP and at 6 months (3 times total). This test will be administered by the Clinical Research Coordinator and scores will be captured. The SPPB is a validated tool composed of a simple battery of objective physical performance tests that involve gait speed, balance and ability to rise from a chair. The SPPB was designed to evaluate balance, gait, strength, and endurance initially in a cohort of 5000 community-dwelling seniors. The tool can be administered in approximately 10 minutes. The SPPB can predict mortality and nursing home admissions among older adults. Interestingly, the measure can also detect a gradient of risk for mortality and nursing home admission among older adults with no current disability.⁹ It also has been shown to predict mortality in cancer survivors.⁵ The tool assesses balance through use of the side-by-side stand, semi-tandem stand, and tandem stand; strength is assessed with the chair stand test and repeated chair stands; and gait speed is evaluated through use of an 8-foot walk test. Scores are assigned for each of the tests and an aggregate score is assigned ranging from 0-12, with higher scores indicating greater physical function. SPPB scores are classified into 4 categories: very low physical function (0-3); low physical function (4-6); moderate physical function (7-9) and high physical function (10-12). An alpha internal consistency of 0.76 has been reported.⁹ The SPPB will be performed twice while the patient is on study, once as a pre-screen enrollment and a second SPPB at completion of the structured exercise program.

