5.0 DATA COLLECTION AND MANAGEMENT

5.1 Registration Process

- Potential patient identified
- Patient signs informed consent and HIPAA form
- Eligibility Screening
- Worksheet documentation note by the primary oncologist giving the patient medical clearance to participate in physical therapy
- Provide patient with Enrollment Handbook [APPENDIX M]
- Register the patient on the study (Oncore)
- Assign a patient study number
- Pend blood work orders
- Documentation of Consent in EPIC
- Schedule twice monthly physical therapy sessions for next 4 months

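### Section 6.1 describes recruitment among screened patients, but 3.1 and 5.1 place consent before the screen, so the figure as written does not measure uptake among patients approached

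*Combined protocol and SAP*

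**What the plan says.** Section 1.2 sets the primary objective as feasibility, assessed by "evaluating recruitment and retention, exercise program adherence, sustainability, adverse events, and implementation challenges". Section 6.1 gives the matching recruitment statistic, "the proportion of screened patients who agree to participate", with a 95% confidence interval and no target.

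Section 3.1 sets out the order of events. Referred patients receive information and "will be asked if they would like to undergo screening for their current level of fitness to determine eligibility for study participation". Then: "Those agreeing to be screened will sign the study consent and HIPAA forms. They will then undergo the SPPB evaluation". The same section equates a failed screen with an SPPB score above 9. Section 4.5.1 also ties the word to the test: "At the time of screening patients will undergo a SPPB". In the 5.1 list, "Patient signs informed consent and HIPAA form" comes immediately before the eligibility screening step.

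Section 3.4 is less clear: "If patients are interested in participating in the study and meet all eligibility criteria, they will sign the consent form and then be assessed". The first half suggests that eligibility is known before consent, while the second half puts the assessment after it.

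On refusals, 3.1 says that "reasons why patients decline participation will be tracked without documenting patient identifiers", using the non-enrollment survey in Appendix A. Section 6.1 does not place those patients in any denominator.

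**The concern.** A recruitment rate should fall when more of the patients who are offered the study say no. If only patients who have already agreed and consented are screened, a rate among screened patients cannot respond to refusals at approach.

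This matters because of what the study is for. Sections 2.1 and 2.6 justify a single-institution feasibility study by the need to work through recruitment and retention problems, and 6.2 looks ahead to a larger multicentre trial. The planners of that trial will need to know how many patients must be approached for each one enrolled. The 6.1 figure, followed as written, would not tell them.

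**Working it through.** The plan states no recruitment rate, target or number approached, so there is no figure to reproduce. The check has two parts.

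**1. Order of events**

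| Step | Source | Does a refusal at approach get this far? |
|---|---|---|
| Informed and asked about screening | 3.1 | Yes; the patient leaves here |
| Signs consent | 3.1, 5.1 | No |
| SPPB and eligibility screen | 3.1, 4.5.1, 5.1 | No |
| Registered | 5.1 | No |

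The 6.1 denominator is formed at the third step, so a refusal at the first step is in neither part of the fraction.

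**2. Illustration**

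From the documents: a maximum of 100 patients recruited (3.6). Assumed, because the documents give no values: 70% of those screened are eligible, uptake at approach is 80%, 50% or 30%, and nobody refuses after the screen.

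- Consented and screened = enrolled / yield = 100 / 0.70 = 143.
- Approached = consented / uptake: 143 / 0.80 = 179; 143 / 0.50 = 286; 143 / 0.30 = 477.
- Exact (Clopper-Pearson) 95% limits for x out of n: the 2.5% quantile of Beta(x, n − x + 1) and the 97.5% quantile of Beta(x + 1, n − x). The upper limit is 1 when x = n.

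| Assumed uptake | Approached | Consented / approached (95% CI) | 6.1 figure if *agree* means consented | 6.1 figure if *agree* means enrolled |
|---|---|---|---|---|
| 80% | 179 | 79.9% (73.3 to 85.5) | 143/143 (97.5 to 100) | 100/143 = 69.9% (61.7 to 77.3) |
| 50% | 286 | 50.0% (44.1 to 55.9) | same | same |
| 30% | 477 | 30.0% (25.9 to 34.3) | same | same |

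The last two columns do not move with uptake. A reader who took either figure as the recruitment rate and combined it correctly with the 70% yield would plan for about 143 approaches per 100 enrolled. The number needed is 179 to 477.

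**Other yields.** At 50% yield, 200 consent and the enrolled version is 100/200 = 50.0% (42.9 to 57.1). At 90% yield, 111 consent and it is 100/111 = 90.1% (83.0 to 94.9). It follows the screening yield and again ignores uptake.

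**Refusal after the screen.** Suppose 5% of eligible patients decline once screened. Then 100 / 0.95 = 105 are eligible and 105 / 0.70 = 150 are screened. The enrolled version falls to 100/150 = 66.7% (58.5 to 74.1), so this kind of refusal does register. The figure is still the same at 30% uptake (500 approached) and at 90% uptake (167 approached).

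**The case against.** The best counter-argument is that the post-consent reading leaves the 6.1 sentence with little content. If every screened patient has already agreed, the proportion is close to 100% by construction and an interval adds nothing. The authors may therefore have meant *screened* loosely, as everyone referred or approached. The terminology is loose elsewhere: 3.2 and 4.5.1 call the SPPB a pre-screen, and 3.4 can be read as an eligibility check before consent. On that reading refusals would count. This objection stands as far as it goes. It shows that the word needs defining, not that 6.1 already measures uptake, because 3.1 and 5.1 use screening for the step after consent.

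A patient could also pass the SPPB and then decline the programme; the example in 3.1, of someone who turns down enrollment because the activity seems too hard, could be such a case. Those refusals would enter the 6.1 figure. Refusals at approach would remain outside it.

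Tracking of decline reasons is planned, and the content of Appendix A is not in the text available for review. The documents therefore show a gap in the reporting denominator, not a missing data source.

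Two stronger inferences are tempting. One is that refusals can never enter the recruitment figure; the undefined term and the possibility of refusal after the screen rule that out. The other is that the planned figure cannot be compared with the roughly 47% participation that 6.1 cites from primary care. The documents do not give the denominator of that 47%, and it is cited in support of the completion criterion, so they cannot settle that comparison.

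**Conclusion.** The point holds with its qualifier: as 3.1 and 5.1 use the word, the 6.1 proportion leaves out patients who refuse at approach. It reflects eligibility and any refusal after the screen, not uptake among those approached. The invariance to uptake follows from the definition and does not depend on the assumed values. The size does depend on them: with 100 enrolled, 70% yield and no refusal after the screen, true uptake of 79.9% or 30.0% would produce the same reported figure.

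A reader might infer that the feasibility conclusion itself is compromised. The documents do not support that. Section 6.1 makes programme completion the primary indicator, with its own denominator of eligible participants and its own 80% criterion, and attaches no threshold to recruitment. The consequence is confined to a descriptive statistic, but one that reports a named component of the primary objective.

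**What to change.** In 6.1, replace the screened denominator and define the terms:

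- **Recruitment:** consented / all patients approached, with an exact 95% CI. Approached means consents plus patients who declined at approach, as recorded through the Appendix A process.
- **Screening yield:** eligible / consented, reported separately.
- **Refusal after the screen:** eligible patients who then decline / eligible, reported separately. These patients have already consented, so they must not be added again as decliners at approach; the log should show the stage of refusal.

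If the authors did intend *screened* to mean everyone approached, one sentence saying so, with 3.4 aligned to 3.1 and 5.1, would settle the matter.

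The cost is mainly wording, with no new patient assessments. The team must confirm that the decline log counts every decliner and does not only collect reasons. Because the log holds no identifiers, a patient who declines and later consents could be counted twice; that limitation should be stated. The reported recruitment figure will probably look less favourable.

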6.2 Secondary Endpoint(s)

For the entire cohort of patients, we will describe CARG GA, number of falls, SPPB, PROMIS HRQL scores at all three time points when the relevant data are collected: baseline, after OEP completion and 6 months. Descriptive statistics of these measurements will be provided as well as graphs in order to help visualize the change over time. The proportion of patients who achieve meaningful change in these scores will be described with 95% CI. Difference from baseline will be tested with Wilcoxon signed rank test or McNemar's test for continuous or categorical variables respectively. Take SPPB for example, with 30 patients a two-sided Wilcoxon signed rank test for paired observations will have at least 80% power to detect a medium effect size of 0.55 (i.e. 0.55 standard deviations) for the differences in scores before and after the OEP. Depending on patient retention rate and completeness of the collected data, linear mixed models with repeated measures might be fitted to quantitatively model the changes, but the modeling analysis will mostly be exploratory due to limited sample size. The correlation between these scores including their baseline values and changes over time and other clinical factors of interest such as age, BMI and performance status will also be evaluated.

For patients undergoing transplant, we will describe the following clinical points of interest: inpatient falls, 90-day hospital readmission rate, and length of inpatient stays. Pre and post OEP changes in CARG GA, SPPB and PROMIS HRQL scores and their potential association with these clinical endpoints will be explored graphically.

Findings will largely be exploratory and will need to be validated in larger subsequent multicenter trial.

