1.3 Secondary Objective(s)

To calculate preliminary effect sizes of the impact of an exercise program in patients with hematologic malignancy undergoing therapy, as measured by:

- Cancer and Aging Research Group (CARG) Geriatric Assessment Tool parameters
- Change in Short Physical Performance Battery (SPPB)
- Number and severity of falls
- Hospital readmission rates (if applicable)
- Length of inpatient stays (if applicable)
- Patient Reported Outcome Measurement Information System (PROMIS) for Health related quality of life (HRQL)
- Correlative analysis of peripheral blood biomarkers of aging and inflammation (p16, inflammatory biomarkers, immunosenescence, miRNA)

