4.5.4 Falls

Falls in patients receiving chemotherapy are associated with a 3-fold greater risk of mortality.⁵¹ Fall and fall severity will be captured as self-report of calendar recorded falls, where patients denote on the calendar day when they had a fall associated with commentary on the event (e.g. fall with abrasion). Calendar recorded events is a valid method of self-reporting fall events and is shown to be more accurate than short term recall in patients with falls.⁵² Falls will be captured twice monthly. Research coordinators may contact the patient

by phone if a fall has occurred to identify the severity of the fall and/or injuries [APPENDIX I].

Inpatient admission falls will be captured per institution guidelines, as all falls are required to be reported to the Quality and Patient Safety Department. Specific information regarding patients enrolled in both as an Exercise Participant and Survey Participant will be gathered. Hospital Injury Level and the National Database of Nursing Quality Indicators (NDNQI) injury level will be captured.

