4.5.5 Exercise Intervention: Otago Exercise Programme (OEP)

Exercise interventions are an established method of improving physiologic and functional performance in older adults. The structured OEP focuses on strengthening, balance retraining, and walking. OEP requires minimal training and can be provided by any physical therapist. OEP requires patient engagement and takes approximately 30 minutes three times weekly, with walking twice weekly. All physical therapist engaged in the protocol are OEP certified. The OEP is 8 physical therapy visits over 4 months. Participants will record daily of walking, exercise and falls in an exercise journal [APPENDIX J].

Patients may require more than 2 sessions monthly of physical therapy according to the physical therapist prescribed recommendations. In this event, exercise logs and fall diaries will be collected at their 1st and 3rd visit monthly. Patients will be reimbursed for their travel at these two visit times only (see Section 5.8).

Table 1. Otago	o Exercise Programme (OEP)				
	Strengthening	Balance Retraining	Walking		
Assessment			Timed Up and Go		
Activity	Five leg muscle strengthening exercises Four levels of difficulty	Twelve balance retraining exercises Four levels of difficulty	Advice about walking		
Intensity	Moderate Challenge 8-10 repetitions before fatigue	Moderate Challenge Each exercise at a level the patient can safely perform	Usual pace with usual walking aid		
Progressions	Increases from one to two sets Increase amount of ankle weight after 2 sets of 10	Supported exercise and unsupported exercise	Walk indoors Advance to walking outdoors when strength and balance have improved		
Length of Exercise Sessions	Approximately 30 minutes total for exercises; Exercises can be divided up over the day		30 minutes; can be split into three 10 minute walks throughout the day		
Home Based Frequency	3 times a week	At least 3 times a week	Twice a week		
Duration	Physical therapy (8 visits, twice monthly, until transplant or 4 months) Transplant physical therapy consult (twice weekly physical therapy consult during transplant admission). Home based exercise throughout their 6 month enrollment.				

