4.5.7 Blessed Orientation-Memory-Concentration Test (BOMC)

The BOMC [APPENDIX L] is a widely used screening test for dementia and evaluation of orientation, registration, and attention. The test allows providers and caregivers to screen for suspected dementia in older patients. It was originally validated on older patients living in both skilled nursing facilities and community-dwelling. The BMOC is a weighted 6-item instrument and takes less than 10 minutes to complete. Scores range from 0-28, and scores greater than 10 are consistent with dementia.

Table 2. Study Measures					
	Study Visit 1: Baseline	Study Visit 2: Completion of OEP*	Study Visit 3: 6 months*		
CARG GA	Х	Х	Х		
SPPB	Х	X	Х		
PROMIS ^a	Х	X	Х		
Falls ^b	Х	X	Х		
OEP Evaluation		X			
Physical Therapy Adherence ^c		Х	Х		
Biomarker ^d	Х	X	Х		
Motivation	Х				
Self-Efficacy	Х	X	Х		
Barriers	Х	X	Х		
Blessed ^e	X*	X*	X*		

*(+/-)30 days; administered monthly; biomarkers (+/-) 14 days

a. PROMIS measures are captured monthly from the time of OEP enrollment (maximum 6 surveys)

b. Falls are captured twice monthly from the time of OEP enrollment via self-report calendar; inpatient falls are captured during hospitalization and are not a self-report.

c. Physical therapy adherence will be captured by the number of visits (inpatient and outpatient) and if patient is achieving the standard based upon the physical therapist assessment (1-achieving the standard, 2-progressing toward the standard, 3-limited progress or not meeting the standard)

d. Blood work will be collected during the study visit with the patients' outpatient hematologist. Attempts will be made to collect blood work during the routine draw, however this is not mandated. Biomarker collection (+/-) 14 days within study visit.

e. If not administered prior to patient's enrollment, the Blessed test will be administered one time at a point after the patient's enrollment in the study.

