5.5 Adverse Events

Individuals will be asked about exercise-related adverse events at the time of study visit. Any exercise-related injuries will be reported to [name] (Principal Investigator). Any reported events will be evaluated for the likelihood that they occurred as a result of exercise. An adverse event is considered serious if it results in any of the following outcomes: 1.) death; 2.) a life-threatening event; 3.) inpatient hospitalization or prolongation of an existing hospitalization >24 hours; 4.) persistent or significant incapacitation or substantial disruption to the participants ability to conduct normal life functions; 5.) congenital anomaly/birth defect; 6.) Important Medical Events (IME) that may not result in death, be life threatening, or require hospitalization but may be considered serious when, based upon medical judgement, the event may jeopardize the patient and may require medical or surgical intervention to prevent one of the outcomes listed in the definition. Serious adverse events related to exercise experienced by patients in this protocol will be reported to the OSU CCC Clinical Trials Office and the Cancer Institutional Review Board (IRB). Information reported will include the number of patients affected, number of patients treated, summary of all adverse events reported to date using the National Cancer Institute Common Terminology Criteria for Adverse Events (CTCAE) version 4.0 grading, a specific list of adverse events requiring expedited reporting to include all serious adverse events [SAEs], and, on an annual basis or as it arises, significant literature reporting developments that may affect the safety of participants or the ethics of the study. Data safety and monitoring activities for each study will continue until all patients have completed their intervention and all patients are beyond the time point at which study-related adverse events would likely be encountered.

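### The protocol does not say that calendar-recorded falls are reconciled with the adverse event record, assessed for relation to exercise, or reported by relatedness

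*Combined protocol and SAP*

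**What the plan says.** **Falls.** Section 1.3 lists "Number and severity of falls" among the measures used to estimate the programme's effect. Section 4.5.4 states that "Fall and fall severity will be captured as self-report of calendar recorded falls", with a comment by the patient on each event. A coordinator may telephone after a fall to establish its severity and any injury. The same section justifies the calendar as a method "shown to be more accurate than short term recall in patients with falls". Table 2, note b, adds: "Falls are captured twice monthly from the time of OEP enrollment via self-report calendar". Section 4.5.5 describes one document for all three items: "Participants will record daily of walking, exercise and falls in an exercise journal". Inpatient falls come from hospital reporting. In the analysis, section 6.2 places falls beside the benefit scores: "we will describe CARG GA, number of falls, SPPB, PROMIS HRQL scores at all three time points when the relevant data are collected".

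**Adverse events.** Section 1.2 makes them part of the primary objective, and section 1.1 includes safe implementation in the hypothesis. Section 5.5 states: "Individuals will be asked about exercise-related adverse events at the time of study visit". Whatever is reported is then judged for a link to exercise. Section 6.1 calls for CTCAE v4.0 severity and "whether any AEs can be attributed to exercise". Table 3, note b, extends attribution to both therapist-led and home exercise. Section 4.5.6 provides for adverse event records while the programme runs, and section 5.4 lists adverse events among items collected at the three visits and/or monthly.

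**The concern.** The protocol collects falls by one route and adverse events by another, and does not state how they connect. The fall route is frequent and, on the protocol's own account, the more accurate. The adverse event route is the one that leads to a judgement about exercise. Its stated question is limited to exercise-related events, so the participant makes the first judgement of cause before anyone on the study team does.

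Participants are aged 60 or over with an SPPB of 9 or less at screening (section 3.2). Their home programme includes balance exercises that progress to unsupported work, and walking (Table 1). Section 4.6 names injury during exercise as a physical risk. Whether falls happen during the exercise itself is something a later multicenter trial would want to know. A total fall count cannot show it, and in a single-arm study there is no comparison group to help.

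**Working it through.** The plan gives no figure for falls. The only power statement in section 6.2 concerns SPPB (30 pairs, 0.55 SD). It reproduces at 81.1% with two-sided alpha 0.05 assumed, and has no bearing on this point.

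**Step 1. Follow a non-injurious fall during home exercise through the plan.**

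| Stage | Fall route | Adverse event route |
|---|---|---|
| Source | Calendar or journal entry by day (4.5.4, 4.5.5) | Question at study visit (5.5); records during the programme (4.5.6); possibly monthly (5.4) |
| Frequency | Twice a month (Table 2, note b) | Three visits, the first before physical therapy starts (3.6) |
| Follow-up | Optional call about severity and injury (4.5.4) | Relation to exercise judged for reported events (5.5) |
| Analysis | Number of falls (6.2) | Severity and attribution (6.1) |

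No row states a transfer from left to right. The fall is certain to be counted in 6.2 if it is entered on the calendar. It reaches 6.1 only if it is also reported as an adverse event.

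**Step 2. Compare the intervals.** The programme has 8 therapy visits over 4 months, so twice-monthly collection gives 2 × 4 = 8 calendar reviews in that time. On the visit schedule alone, one adverse event question (visit 2, at programme completion) covers the same 4 months. If the monthly option in section 5.4 is used, there are about 4. Either way, the more frequent source is the one not stated to feed attribution.

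**Step 3. What a separate summary would deliver.** Let x be the participants with at least one during-exercise fall among n. The exact (Clopper-Pearson) 95% limits are:
- lower = the 0.025 quantile of Beta(x, n − x + 1), or 0 if x = 0
- upper = the 0.975 quantile of Beta(x + 1, n − x)

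For x = 0 the upper limit reduces to 1 − 0.025^(1/n). With n = 30 this is 1 − 0.025^(1/30) = 11.6%. With n = 100 it is 1 − 0.025^(1/100) = 3.6%.

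| x / n | Exact 95% CI |
|---|---|
| 0/30 | 0 to 11.6% |
| 3/30 | 2.1 to 26.5% |
| 0/100 | 0 to 3.6% |

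Here 30 is the number in the section 6.2 power statement and 100 is the enrolment maximum in section 3.6. The values of x are illustrations, not forecasts.

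**The case against.** The strongest reply is that the adverse event provisions are wider than the visit question. Section 4.5.6 keeps records throughout the programme, section 5.4 allows monthly collection, section 5.5 assesses any event that is reported, and Table 3 covers home exercise. Coordinators also gather exercise logs and ask about problems exercising at home (section 4.3). The fall questionnaire and the diary (Appendices I and J) are listed as attached, but their content was not available. Either may already ask what the patient was doing, and the calendar comment could hold it. All of this stands. It means the link may exist in practice. It does not supply a statement that calendar falls are reconciled, attributed and reported.

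Three stronger readings are tempting, and the documents do not support them.

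- *A reader might infer that falls are treated solely as a benefit and cannot be classed as exercise-related.* The provisions above contradict that: a fall reported as an adverse event would be assessed.
- *A reader might infer that the 6.2 total is wrong because caused falls offset prevented ones, and might size this from the 30–60% reduction in section 2.2.* A total is a legitimate measure of net effect, and section 6.2 calls its findings largely exploratory. The cited reduction is in the risk of falls, so on its face any falls provoked by the exercise are already in it. It cannot be read as a gross benefit to set against caused falls.
- *A reader might want to test for excess by setting 2.5 prescribed hours a week (3 × 0.5 + 2 × 0.5) against waking time.* The result depends on the denominator. Take 30 falls (assumed) and one-sided p < 0.025. With 112 waking hours (assumed), the threshold is 4 falls during exercise. With 40 to 20 upright hours (assumed), the expected number is 30 × 2.5/40 = 1.9 to 30 × 2.5/20 = 3.8, and the threshold is 6 to 9. The documents give no basis for choosing.

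**Conclusion.** The point holds as a gap in data handling and reporting. The protocol body does not say that calendar falls are reconciled with the adverse event record, assessed for relation to exercise, or shown separately by relatedness. A during-exercise fall can therefore be in the 6.2 count and absent from the 6.1 safety summary.

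The number of falls affected cannot be derived, because the documents give neither an expected fall count nor a share occurring during exercise. The conclusion rests on the visible text. If Appendix I or J already records activity, the collection part is met, and only the reconciliation and reporting steps remain to be stated. The matter should be settled before data collection, since what a patient was doing when they fell may not be recoverable later.

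**What to change.** 1. **Sections 4.5.4 and 5.5.** At each twice-monthly diary review, record for every fall, outpatient or inpatient, whether it occurred during OEP exercise or walking, at home or therapist-led. Reconcile each fall with the adverse event record for CTCAE grade and attribution. Section 5.4 ties diary collection to OEP appointments, while home exercise continues to 6 months, so state the contact at which this is done once the therapy visits end.
2. **Section 6.1.** Report the number of during-exercise falls and the proportion of participants with at least one, with an exact 95% CI.
3. **Section 6.2.** Keep the total number of falls and show it split into during-exercise and other falls.
4. If Appendix I or J already has an activity field, cite it in place of a new one.

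**Cost.** One extra item at a review that already takes place and a few table rows, with no added study visit or staff. A few more events may be classed as exercise-related, so the reported safety profile may look slightly less favourable.
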